**Protocol Number: 64041575RSV2002**

**Standardized Questionnaire for Use During Scheduled Study Site Visits and Monthly Phone Calls Between Study Site Visits**

### **General Instructions for the Study Site**

- The questionnaire needs to be completed in its entirety by the study site through parent/caregiver interviews during scheduled study site visits (entry visit, 3, 6, 12, 18, and 24 months) and monthly phone calls between study site visits.
- When referring to wheezing, eczema, and allergic rhinitis with the parent/caregiver, please use simple terminology provided in the definitions section (see below).
- Records need to be obtained from the subject's doctor or health care provider to confirm the diagnosis of asthma, eczema, and allergic rhinitis.
- Please keep completed questionnaires and wheezing/medication parent/caregiver cards as part of the study file.

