## **2.1.2. Endpoints**

### **Primary Endpoints**

The primary endpoints are:

- Clinical diagnosis of asthma within the first 2 years after the RSV infection, as diagnosed by a physician and reported by the parent/caregiver.  
All medical information needed to confirm the diagnosis of asthma needs to be collected by the study site personnel.
- Percentage of wheezing days within the first 2 years after the RSV infection, based on information reported by the parent/caregiver.

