**Section B: Questions About Asthma**

**Important note for the study site: If on a previous questionnaire, the parent/caregiver indicated that the child has been diagnosed with asthma, please proceed to Section C.**

Please remind the parent/caregiver that the date of last interview was:

\_\_/\_\_/\_\_\_\_ (DD/MM/YYYY)

**1. Since the last study site visit/telephone call, has the child been diagnosed with asthma by a doctor or health care provider?**

No

Yes

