**a. When was the child diagnosed with asthma by a doctor or health care provider?**

Date of asthma diagnosis: \_\_/\_\_/\_\_\_\_ (DD/MM/YYYY)

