**Section C: Questions About Eczema**

**Important note for the study site: If on a previous questionnaire, the parent/caregiver indicated that the child has been diagnosed with eczema, please proceed to Section D.**

Definition of eczema: dry, itchy, scaly patches on the skin

Please remind the parent/caregiver that the date of last interview was:

\_\_/\_\_/\_\_\_\_ (DD/MM/YYYY)

**1. Since the last study site visit/telephone call, has the child been diagnosed with eczema by a doctor or health care provider?**

No

Yes

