**Section D: Questions About Allergic Rhinitis**

**Important note for the study site: If on a previous questionnaire, the parent/caregiver indicated that the child has been diagnosed with allergic rhinitis, please proceed to Section E.**

Definition of allergic rhinitis: inflammation of the nasal passages due to allergies and characterized by episodes of sneezing, stuffy nose, often accompanied by itching of the eyes and nose.

Please remind the parent/caregiver that the date of last interview was:

\_\_\_/\_\_\_/\_\_\_ (DD/MM/YYYY)

**1. Since the last study site visit/telephone call, has the child been diagnosed with allergic rhinitis by a doctor or health care provider?**

No

Yes 

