5. EFFICACY

5.1. Primary Efficacy Endpoint(s)

5.1.1. Definition

The primary endpoints are:

1. Clinical diagnosis of asthma within the first 2 years after the RSV infection, as diagnosed by a physician and reported by the parent/caregiver. This will be derived based on the completed study questionnaires at each visit/telephone call until the final visit. It is either “Yes” or “No”.
2. The percentage of wheezing days in a subject within the first 2 years after the RSV infection will be calculated as:

$$\text{Percentage of wheezing days} = \left(\frac{\text{number of wheezing days}}{\text{day of study completion} - \text{day of informed consent} + 1} \right) * 100$$

The percentage will be rounded to the nearest integer. Number of wheezing days is the sum of all days that were reported in the Monthly visit reports. The day of informed consent is the informed consent of the RSV2002 study.

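### The questionnaire stops asking about asthma, eczema and allergic rhinitis once a caregiver reports a diagnosis, whether or not records confirm it

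*Protocol*

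**What the plan says.** The general instructions in Protocol Attachment 2 (the standardized paper questionnaire) tell the site to obtain records from the child's "doctor or health care provider to confirm the diagnosis of asthma, eczema, and allergic rhinitis". Protocol Section 2.1.2 attaches a similar duty to the primary asthma endpoint: "All medical information needed to confirm the diagnosis of asthma needs to be collected by the study site personnel". Sections 9.1.2 and 9.1.3 extend it to all three diagnoses, at the entry visit and at every later visit and call.

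The skip notes on the form read differently. Section B: "If on a previous questionnaire, the parent/caregiver indicated that the child has been diagnosed with asthma, please proceed to Section C". Section C: "If on a previous questionnaire, the parent/caregiver indicated that the child has been diagnosed with eczema, please proceed to Section D". Section D: "If on a previous questionnaire, the parent/caregiver indicated that the child has been diagnosed with allergic rhinitis, please proceed to Section E". The item that records the asthma date ("When was the child diagnosed with asthma by a doctor or health care provider") lies inside Section B, and its counterparts lie inside Sections C and D.

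On the analysis side, SAP 5.1.1 says of the asthma endpoint: "This will be derived based on the completed study questionnaires at each visit/telephone call until the final visit". The result is a single Yes or No per child. SAP Table 3 derives eczema and allergic rhinitis in the same way from Sections C and D. All three are summarized as proportions with Wilson 95% intervals (SAP 5.1.3 and 5.3.2). SAP 2.4 reports 7 enrolled subjects.

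**The concern.** The confirmation duty treats a caregiver's Yes as provisional, while the skip note treats it as final. Followed as written, one early Yes closes the section, including its date item, at every later contact, even if the records then show that no diagnosis was made.

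The documents leave room for this to happen. Section B accepts a diagnosis by a doctor or another health care provider, whereas the endpoint requires a physician. The medical resource footnote to the Time and Events Schedule counts physician assistants and nurse practitioners as providers. A truthful Yes can therefore fall outside the endpoint definition. The form also gives caregivers a plain-language definition of wheezing, eczema and allergic rhinitis, but none of asthma.

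At stake is the correct classification of a primary endpoint, and of two exploratory items that the SAP adds, in a very small study.

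**Working it through.** No figure in the plan bears on this point, so there is none to reproduce. The check is a reading of the rules, followed by a calculation of scale.

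**1. Trigger against confirmation.** The skip is triggered by the caregiver's earlier report. The confirmation duty calls for provider records. Neither document says what happens when the two disagree: there is no reset, no reopening and no field for an unconfirmed report.

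**2. How long a section can stay closed.** Site visits fall at 3, 6, 12, 18 and 24 months after entry (5 visits), with monthly calls in between (24 − 5 = 19 calls). That gives up to 24 contacts after entry.

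**3. What happens to a child with an early Yes.** Any later diagnosis in the table is a true one within the 2 years.

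| Case | Records confirm the early Yes? | Later true diagnosis? | SAP as written | True status | If unconfirmed answers were set aside |
|---|---|---|---|---|---|
| A | yes | not relevant | Yes | Yes | Yes |
| B | no | no | Yes (false positive) | No | No |
| C | no | yes | Yes (right status, wrong date) | Yes | No on the questionnaire (case missed) |

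In case B the skip blocks nothing. The error comes from the absence of a confirmation rule. In case C the skip does block the later diagnosis and its date, but this changes the Yes/No status only under a rule that sets unconfirmed answers aside. Neither document contains such a rule.

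**4. Scale.** Input: n = 7 (SAP 2.4). One child is 1/7 = 14.3 percentage points overall. The Wilson interval, with z = 1.96, is

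(p + z²/2n ± z·√(p(1 − p)/n + z²/4n²)) / (1 + z²/n)

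- 0/7: 0%, 95% CI 0.0 to 35.4%
- 1/7: 14.3%, 95% CI 2.6 to 51.3%

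The split by arm is not given. Over assumed arm sizes of 2 to 5:

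- 1/2: 50%, 95% CI 9.5 to 90.5%
- 1/5: 20%, 95% CI 3.6 to 62.4%

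**5. What cannot be computed.** The documents do not say how often an early report goes unconfirmed, so no expected number of affected children can be given.

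**The case against.** A reader might infer that the asthma endpoint is wrong for such a child however the early Yes is treated. The documents do not support that. The endpoint is one Yes or No, and no time-to-diagnosis analysis is planned. In case C the child ends as Yes, which is correct, and the wrong date changes no planned proportion. Setting unconfirmed answers aside in case B also gives the right status.

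A reader might also infer that a later diagnosis is lost to the study. That too goes beyond the text. The duty to collect confirming information at each contact has no skip. Respiratory illness adverse events are reportable throughout (Protocol 9.4). SAP 6.1.1 says eczema and allergic rhinitis were also collected as adverse events. The medication card asks for the indication, and respiratory medical encounters are recorded. It stands that these routes may show the event. It also stands that the SAP names the questionnaire, not these sources, for the three diagnoses.

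The general instructions add "The questionnaire needs to be completed in its entirety by the study site", which pulls against skipping. But the section notes are more specific and are marked as important for the site, so a site would reasonably follow them. Protocol 17.5 provides for corrections to the eCRF, but does not say whether an earlier Yes on the paper form may be corrected after records fail to support it.

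Finally, SAP Section 3 says the project was stopped, and the analysis is descriptive without testing. A revised form cannot recover contacts already made. This limits the value of the form change but leaves the SAP change useful.

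**Conclusion.** The point holds in a limited form. The skip rule conflicts with the protocol's own confirmation step, and neither document resolves the conflict. Under the SAP as written, the direct effects are a false positive that stays in the asthma count (case B) or a right status with a wrong date (case C). A true case is missed on the questionnaire only if unconfirmed answers are set aside, which is not specified, and even then other study records may show it.

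One misclassified child moves the overall proportion by 14.3 percentage points, or an arm by 20 to 50 points if arms hold 5 to 2 children, which is an assumption. Whether any of the 7 children is affected cannot be told from the documents. Eczema and allergic rhinitis carry less weight, since they are exploratory items in the SAP and are not among the protocol's listed endpoints. This is a cheap improvement to the handling of a primary endpoint, and does not by itself show that any result is wrong.

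**What to change.** - **Form.** Reword the skip notes in Sections B, C and D along these lines: *If a diagnosis was reported on an earlier questionnaire and has been confirmed from records, go to the next section; otherwise ask again.* Add one field to each section: *confirmed by records: yes / no / pending, date*.
- **SAP 5.1.1 and Table 3.** Count record-confirmed diagnoses dated within 2 years of the RSV infection, and show the caregiver-reported count as a sensitivity summary. The date limit is needed because, on the protocol's schedule, entry may be up to 3 months after randomization and the last visit 24 months after entry, so contacts can run to about 3 + 24 = 27 months after randomization.
- **Contacts already made.** Apply the same rule by checking the collected records of the 7 children.

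The cost is one reworded line and one field in each of three sections, a short addition to the SAP, one repeated yes/no question per contact until confirmation, and a small record check. The change does move the main count from caregiver-reported to record-confirmed diagnoses, which is why the reported count should stay visible beside it.

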### **Definitions**

Wheezing: whistling sounds in the chest

Eczema: dry, itchy, scaly patches on the skin

Allergic rhinitis: inflammation of the nasal passages due to allergies

**Date of current interview:** \_\_/\_\_/\_\_\_\_ (DD/MM/YYYY)

**Patient ID:** \_\_\_\_\_

### Section A: Questions About Wheezing

Definition of wheezing: whistling sounds in the chest

Please remind the parent/caregiver that the date of last interview was:

\_\_/\_\_/\_\_\_\_ (DD/MM/YYYY)

**1. Since the last study site visit/telephone call, did the child have any wheezing?**

No → go straight to Section B

Yes ↓

- a. Please provide the days of wheezing and missing days of wheezing in the calendar below.

____/____ (Month/Year)						
Monday	Tuesday	Wednesday	Thursday	Friday	Saturday	Sunday

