## 3. STUDY DESIGN AND RATIONALE

### 3.1. Overview of Study Design

This is a global multicenter, blinded, LTFU study to evaluate the incidence of the clinical diagnosis of asthma and the frequency of wheezing in infants and children (otherwise healthy or with underlying comorbidities for severe RSV) who have completed their treatment course and their last planned study-related visit in a previous Phase 2 study, 64041575RSV2004, in which they received lumicitabine or placebo for the treatment of RSV infection. Subjects will be followed for at least 2 years following treatment. Participation in this LTFU study is optional for study sites. This LTFU study will be offered to subjects of Study 64041575RSV2004 if their site decides to participate in the LTFU.

No study drug will be administered in this study. Subjects may be enrolled within 3 months after randomization in Study 64041575RSV2004. Assessments will be performed at the time points specified in the [Time and Events Schedule](#). The last visit of Study 64041575RSV2004 (ie, Day 28) may be combined with the entry visit of this LTFU study.

Parents/caregivers will be provided with a wheezing parent/caregiver card and a medication parent/caregiver card, both of which should be completed on a daily basis. These parent/caregiver cards will serve as reminder cards when a study site responsible person interviews the subject’s parent/caregiver in order to complete a standardized paper questionnaire. The questionnaire will be completed by a study site responsible person at each study site visit as noted in the [Time and Events Schedule](#) and during a monthly telephone call (calendar month  $\pm 7$  days) between study site visits (see Section 9.1.3).

An unblinded interim analysis will be performed when all subjects from the first season in Study 64041575RSV2004 who are enrolled in this LTFU study complete the 18 months follow-up assessment of this LTFU study. Sites and the parents/caregivers of subjects will remain blinded. This interim analysis will serve to evaluate the need for an extension of the follow-up period (see Section 11.6).

The planned total study duration for each subject will be 24 months unless the decision is taken to extend the duration of follow-up in this study, based on the interim analysis.

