### **9.1.3. Study Period**

No study drug will be administered.

The medical follow-up of the subjects will be performed according to the local standard of care during the assessment period.

At each study site visit (3, 6, 12, 18, and 24 months after entry visit) as noted in the [Time and Events Schedule](#) and during a monthly telephone call (calendar month  $\pm 7$  days), a clinical questionnaire (see [Attachment 2](#)) will be completed by a study site responsible person, by interviewing the subject’s parent/caregiver, to collect the following information:

- Wheezing.  
The parent/caregiver will be provided with a wheezing parent/caregiver card to be completed daily (see [Attachment 3](#)) which will aid the site responsible person in completing the questionnaire.
- Diagnosis of asthma, eczema, and allergic rhinitis. All medical information needed to confirm the diagnosis of asthma, eczema, and allergic rhinitis needs to be collected by the study site personnel.
- Impact of the subject’s health status on normal daily activities for subjects, parents/caregivers, and other family members.

Medical resource utilization data will be collected throughout the study.

Parents/caregivers will also be provided with a medication parent/caregiver card to record medication use on a daily basis (see [Attachment 4](#)).

Parents/caregivers will be required to return the completed wheezing and medication parent/caregiver cards to the study sites every 3 months (eg, in person or by mail/email/fax when no study site visit is scheduled).

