**BACK****How to use the wheezing card**

- This card is to help you remember which days your child had wheezing; that is a day when you heard whistling sounds in the child's chest during breathing.
- Each day at bedtime:
  - If the child had wheezing that day, put a "1" in the box for the date.
  - If the child did not have wheezing that day, put a "0" in the box for the date.

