**How to read the wheezing card during the phone calls with the study coordinator**

- Provide the days the child had wheezing since the last study site visit/phone call.
- Provide the days the child had no wheezing since the last study site visit/phone call.

**Please bring all wheezing cards with you to the study site visits/phone calls! Please also bring the wheezing cards every 3 months to the study site according to local procedures (eg, by mail, by scan/email, in person, etc.)!**

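### The questionnaire logs missing diary days only when wheezing is reported, which limits how the SAP's elapsed-day wheezing percentage can be corrected

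*Protocol*

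**What the plan says.** **Questionnaire (Protocol Attachment 2, Section A, question 1).** If the caregiver reports no wheezing since the last contact, the interviewer is told to "go straight to Section B". Only the Yes branch leads to item 1a: "Please provide the days of wheezing and missing days of wheezing in the calendar below".

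**Daily card (Protocol Attachment 3).** Each date gets a 1 for wheezing. For the other case the instruction is "If the child did not have wheezing that day, put a" 0 in the box, so a blank differs from a wheeze-free day. At calls the caregiver is also asked to "Provide the days the child had no wheezing since the last study site visit/phone call".

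**What happens to the cards.** Protocol 3.1 gives them a supporting role: "These parent/caregiver cards will serve as reminder cards when a study site responsible person interviews" the caregiver. Protocol 9.1.3 adds: "Parents/caregivers will be required to return the completed wheezing and medication parent/caregiver cards to the study sites every 3 months". Sites are told "Please keep completed questionnaires and wheezing/medication parent/caregiver cards as part of the study file" (Attachment 2, general instructions). Protocol 17.4 treats visit and call data entered in the eCRF and questionnaire as source data. No section says that card zeros or blanks are entered for analysis.

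**Analysis (SAP 5.1.1).** For the numerator, "Number of wheezing days is the sum of all days that were reported in the Monthly visit reports". The denominator is study completion day minus consent day plus 1, with no deduction for missing days. SAP 5.2.1 drops the two missing-data imputations of Protocol 11.3.2 because so few subjects enrolled; SAP 2.4 gives that number as 7.

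**The concern.** Whether a missing day is recorded on the questionnaire depends on the outcome being measured. A No interval with a half-empty card looks the same as a fully observed wheeze-free interval; a Yes interval with the same gaps does not. The card was designed to make that distinction for every day, but the form has nowhere to put it after No.

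This matters because of the SAP denominator. Dividing by all elapsed days treats every unrecorded day as wheeze-free, which pulls the primary percentage down. The natural repair is to divide by days of known status. If the known days come from the questionnaire alone and are pooled over follow-up, the repair is uneven: it removes few missing days for a child who seldom wheezes and many for one who wheezes often. With the imputations dropped, the SAP has no other check on missing days.

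**Working it through.** The documents state no missing-day rate and no figure that can be reproduced here, so the size is an illustration.

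**Assumed inputs (not in the documents).** 24 months of 30 days, so T = 720. A share m of card days is blank in every month, unrelated to wheezing, and wheezing on a blank day is not reported at interview. A share w of months is answered Yes.

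**Ratio of each version to the true percentage**

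- SAP 5.1.1, elapsed days: T(1 − m)/T = 1 − m.
- Pooled known days from the questionnaire: (1 − m)/(1 − w·m), because only blanks in Yes months are removed.
- Known days from the cards: (1 − m)/(1 − m) = 1.

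| m | SAP | Questionnaire, w = 0.25 | Questionnaire, w = 0.75 | Cards |
|---|---|---|---|---|
| 10% | 0.90 | 0.90/0.975 = 0.923 | 0.90/0.925 = 0.973 | 1 |
| 20% | 0.80 | 0.80/0.95 = 0.842 | 0.80/0.85 = 0.941 | 1 |
| 30% | 0.70 | 0.70/0.925 = 0.757 | 0.70/0.775 = 0.903 | 1 |

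**Two children at m = 20%**

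- Child A: 6 Yes months with 5 true wheezing days each, 30/720 = 4.17%. Reported days are 30 × 0.8 = 24.
  - SAP: 24/720 = 3.33%.
  - Questionnaire, pooled: blanks removed are 6 × 30 × 0.2 = 36, so 24/684 = 3.51%.
  - Cards: 24/576 = 4.17%.
- Child B: 18 Yes months with 10 true wheezing days each, 180/720 = 25.00%. Reported days are 180 × 0.8 = 144.
  - SAP: 144/720 = 20.00%.
  - Questionnaire, pooled: blanks removed are 18 × 30 × 0.2 = 108, so 144/612 = 23.53%.
  - Cards: 144/576 = 25.00%.

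**Averaging monthly percentages instead of pooling.** Use wheezing days over known days in Yes months and 0% in No months.

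- Child A: 4/24 = 16.7% in each Yes month; 4/24 × 6/24 = 4.17%.
- Child B: 8/24 = 33.3% in each Yes month; 8/24 × 18/24 = 25.0%.

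Both true values are recovered, provided every No is correct for the whole interval.

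**The case against.** A reader might infer that the primary percentage cannot be put on a known-day basis at all. The documents do not support that. The cards hold a daily 1 or 0, go back to the site every 3 months and are filed, so known days can be rebuilt wherever cards were completed and returned. Even without them, the monthly average above works if the No answers are trusted, and a monthly percentage is already a planned secondary endpoint.

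A reader might also take the gap between 0.842 and 0.941 (a ratio of about 1.12) as a spurious difference in the planned analysis, or between treatment groups. It is neither. The SAP formula gives 0.80 for both children at 20% blank, so no relative gap arises there. The gap belongs to a pooled questionnaire-based denominator that neither document proposes, and it contrasts two assumed children, not two groups.

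Nor can one say that gaps in No intervals are never captured anywhere. The Time and Events Schedule includes card verification at site visits, and the eCRF completion and monitoring guidelines are not in the documents.

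Finally, with 7 subjects, no testing and a stopped project (SAP 3), rewording the form alone would alter no planned result.

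All of this stands. What it leaves untouched is that the form hides gaps in No intervals, that the SAP treats blank days as wheeze-free, and that reliance on the No answers cannot be checked without the cards.

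**Conclusion.** The point holds in a limited form. On the questionnaire, missing days are visible only where wheezing was reported. The planned primary percentage is understated because of its elapsed-day denominator, by the factors in the SAP column of the table (0.70 to 0.90 for 30% to 10% blank). The skip does not alter today's figure; it restricts how that figure can be corrected from questionnaire data.

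The size rests on the assumed blank rate, on blanks being unrelated to wheezing, and on wheezing during blank days going unreported. If caregivers recall such days at interview, the understatement is smaller. If wheezing days are more likely to be left blank, bias remains even with the cards. The consequence is confined to descriptive estimates, although with 7 children one child's value can move a group mean.

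**What to change.** 1. For the 7 enrolled children, enter each day's status (1, 0 or blank) from the wheezing cards that were returned.
2. Report the percentage of wheezing days over days with known status, give the number of known days per child, and keep the elapsed-day version as a sensitivity analysis.
3. List the intervals where the card and the Yes/No answer disagree.
4. Where cards are unavailable, average the monthly percentages as shown above and state that this relies on the No answers being complete. SAP Table 2 names the numerator of the monthly percentage but not its denominator, so known days should be written in.
5. In any reuse of the form, ask for missing days whatever the answer to question 1.

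The cost is a short SAP change and one-off data entry of at most 7 × 24 = 168 monthly cards. That is an upper figure, since the documents do not show that follow-up, completion and return were complete. No new data collection is needed.
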